Power Calculations for Hypothesis 1. In this study with 108 participants in the supplement group and 54 in the placebo group, there will be >90% power to detect a difference in stress levels, at any particular visit, of the same magnitude as that observed in our preliminary study at 30 weeks (27.5+/-3.4 vs. 29.3+/-3.1), using a two-sided test at the 0.05 significance level. Additionally, with 162 participants, there will be 80% power to detect a correlation of 0.22 between changes in DHA levels in the blood versus changes in perceived stress. For the cortisol response to the TSST, there will be >95% power to detect a difference in AUCs at a given visit of the same magnitude as that found in our preliminary study at 30 weeks (-4.5+/-3.9 vs. -8.1+/-6.1; negative values indicating net decreases rather than increases), using a two-sided test at the 0.05 significance level.

Hypothesis 2. DHA supplementation during pregnancy will improve infant birth and developmental outcomes among African American women living in urban poverty.

Infants of mothers who receive DHA supplementation will have longer gestations, higher birth weights, more optimal neurodevelopmental outcomes as measured by the NBAS and Bayley Scales of Infant Development, and more optimal maternal reports of temperament in comparison to infants whose mothers did not receive DHA supplementation. We will use ANOVA (e.g. birth weight) or rmANOVA (e.g. NBAS) to test for significant differences between treatment groups. For categorical infant outcomes, such as pre-term birth or low Apgar scores, logistic regression will be employed. We will also test the association between level of DHA in blood at the last prenatal visit and/or change in DHA levels from baseline and infant outcomes using linear (e.g. birth weight or change in NBAS) or logistic (e.g. pre-term birth) regression.

Transformations of the continuous dependent measures will be performed to stabilize the variance across groups if needed.

Infants of mothers who received DHA supplements will demonstrate more modulated cortisol response to the NBAS and still-face paradigm, with a lower peak response and a steeper slope from peak to recovery, in comparison to infants whose mothers did not receive DHA supplementation. Analyses will be performed as described for Hypothesis 1.

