Infant gender, mothers' postpartum stress, depression, and anxiety levels will be compared between those received DHA supplements during pregnancy and those who did not using ANOVA. If significant differences are found, then these factors will also be controlled for in the analyses. If time of collection is associated with cortisol values, then this will also be controlled for in the analyses. However, since a circadian rhythm is not firmly established prior to the age of 6 months, we do not expect to have to control for time of day at 1 and 4 months.

Power Calculations for Hypothesis 2. Based on published data on maternal report of difficult temperament in infants using the ICQ (Keenan et al., 1998), the estimated SD for the ICQ in the proposed study is 7.8. With 108 participants in the supplement group and 54 in the placebo group, there will be 80% power to detect a difference in the ICQ of 3.7 between the two groups at a given visit, using a two-sided test at the 0.05 significance level.

The SD for 30–minute post-test cortisol levels in response to the FFSF paradigm was reported as 0.4 μ g/dL (Hayley & Stansbury, 2003). If we assume a similar amount of variability in peak responses to the FFSF, with 108 participants in the supplement group and 54 in the placebo group, there will be 80% power to detect a difference of 0.19 μ g/dL between the two groups, using a two-sided test at the 0.05 significance level.

[figure not shown]
In addition, there will be approximately 90% power to detect a difference in birth weights of the same magnitude as that observed in our preliminary study (3174+/-480 vs. 2889+/-549 g), using a two-sided test at the 0.05 significance level.

Hypothesis 3. The association between DHA supplementation during pregnancy and infant outcomes will be partially mediated by reductions in maternal perceived stress, stress reactivity during pregnancy.

Mediation will be tested using the Baron and Kenny approach (Baron & Kenny, 1986) with the following general model:

$$g(E(Y_i)) = \alpha + \beta M_i + \omega T_i + \lambda Z_i$$

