 Y_i is an outcome for infant i, g is a link function (e.g. logistic or identity), M_i is a maternal stress measure at the final prenatal visit for the mother of infant i, T_i is treatment group (e.g. 0=placebo vs. 1=active; average DHA level in the blood across prenatal visits), and Z_i is a vector of additional covariates such as infant gender, mothers' postpartum stress, depression, or anxiety. The change in ω due to adding maternal stress to the model provides an estimate of the proportion of the treatment effect due to this factor; if ω is still significant but the magnitude is reduced, this would provide evidence for partial mediation. For infant outcomes collected at multiple visits, the initial approach will be to use data from the last visit, but longitudinal approaches may be considered depending on the results from the initial analyses. To provide greater power for detecting such effects, bootstrapped confidence intervals will be examined. Since multiple measures of maternal stress will be collected, the model may be extended to permit multiple mediators.

Power Calculations for Hypothesis 3. Based on simulation results presented in Fritz et al. and the SAS program provided at http://ripl.faculty.asu.edu/wp-content/uploads/2013/02/baronkenny3.txt, 162 subjects will provide sufficient power (>80%) to detect the following effects based on Cohen's criteria. As shown in Figure 6 and Table 2, the study with 162 subjects will be sufficiently powered (>80%) to detect medium effects for the α and β paths and small effects for the direct effect (scenario 1), or small-medium effects for the α and β paths and medium effects for the direct effect (scenario 2), which is plausible based on the effects found in the preliminary study.

Table 2: Overview of power for mediation hypothesis

	α path	β path	Direct effect	
scenario 1	medium	medium	small	
scenario 2	small-medium	small-medium	medium	

Missing data. Missing data is not expected to be a major issue based on retention rates from the preliminary study. The last observation carried forward (LOCF) approach for missing data will be employed. Sensitivity analyses using complete-cases only will also be performed and the results using the two approaches compared. Related to this, treatment non-compliers will be included in the primary analysis based on the intent-to-treat (ITT) principle.

Timeline for participant visits

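### Hypothesis 3: for binary infant outcomes, the change in the logistic treatment coefficient is not the proportion mediated; for continuous outcomes it is, but the decision clause should be tied to a named test

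*Combined protocol and SAP*

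**What the plan says.** Under Hypotheses and Analyses, Hypothesis 3 sets out a single model for all infant outcomes, in which "g is a link function (e.g. logistic or identity"). M is a maternal stress measure at the final prenatal visit, T is treatment and ω is its coefficient.

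- Framework: "Mediation will be tested using the Baron and Kenny approach".
- Estimator: the change in ω when M is added "provides an estimate of the proportion of the treatment effect due to this factor". No distinction is made between links.
- Conclusion: "if ω is still significant but the magnitude is reduced, this would provide evidence for partial mediation".
- Uncertainty: "To provide greater power for detecting such effects, bootstrapped confidence intervals will be examined". The quantity to be bootstrapped and the rule for acting on the interval are not stated.

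Logistic outcomes are a planned part of this. Hypothesis 2 says: "For categorical infant outcomes, such as pre-term birth or low Apgar scores, logistic regression will be employed".

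**The concern.** On the identity scale, a treatment coefficient changes after adjustment for M only to the extent that treatment and M are associated. On the logit scale it also changes because M explains outcome variation. The log odds ratio averaged over M is closer to zero than the log odds ratio at fixed M, even when M is perfectly balanced between arms. The plan's difference for a binary outcome therefore mixes mediation with a scale effect of the opposite sign.

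At stake is the mediation finding for pre-term birth and Apgar. A real pathway through maternal stress could be reported as smaller than it is, as absent, or as a negative proportion.

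A second and lesser matter applies to either link. The sentence on partial mediation asks only that ω be smaller and still significant. It does not say that the fall in ω must itself be distinguishable from chance.

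**Working it through.** **The plan's own figure.** Power Calculations for Hypothesis 3 states more than 80% with 162 subjects. Numeric path sizes are not given. Assuming 0.39, 0.26 and 0.14 for medium, small-medium and small, with 108 and 54 women and the full Baron-Kenny steps, simulation gives about 93% for scenario 1 and 82% for scenario 2, so the statement reproduces. With 0.3, 0.2 and 0.1 it would be about 60% and 51%. The power figure is not in dispute.

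**Logistic link, no mediation.** Inputs:
- Pilot pre-term rates of 22% (placebo) and 13% (supplement), from Preliminary support for hypotheses. Log OR = ln[(0.13/0.87)/(0.22/0.78)] = -0.635; a conditional ω of -0.63 is used.
- Placebo risk p0 of 22%, with 16% as a lower alternative (the pilot rates pooled 2:1: (2 × 13 + 22)/3 = 16).
- Effect b of stress on the outcome, in log-odds per SD. The documents do not give it; 0.5, 1.0 and 1.5 are assumed.
- M is standard normal and independent of treatment, so the true proportion mediated is 0.

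Formulas: p(T) = ∫ expit(a + ωT + bM) φ(M) dM, with a chosen so that p(0) = p0. The coefficient without M is ω_tot = logit p(1) - logit p(0). The plan's proportion is (ω_tot - ω)/ω_tot.

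Worked case, p0 = 0.22 and b = 1: a = -1.510, p(1) = 0.1399, ω_tot = -0.551. The proportion is (-0.551 + 0.63)/(-0.551) = -14%.

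| b per SD | ω_tot, p0 = 16% | proportion | ω_tot, p0 = 22% | proportion |
|---|---|---|---|---|
| 0.5 | -0.613 | -3% | -0.608 | -4% |
| 1.0 | -0.564 | -12% | -0.551 | -14% |
| 1.5 | -0.498 | -27% | -0.481 | -31% |

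Fixing the marginal rates at 22% and 13% instead gives -3.6%, -14% and -30%.

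**Logistic link, true mediation.** Let treatment also lower stress by 0.3 SD (assumed), with p0 = 22%.

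| b per SD | plan's proportion | natural indirect share, log-OR scale | natural indirect share, risk scale |
|---|---|---|---|
| 0.5 | 16% | 19% | 15–16% |
| 1.0 | 23% | 33% | 27% |
| 1.5 | 25% | 43% | 36% |

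**Would the bootstrap cure it?** Only if applied to the right quantity. With no effect of treatment on M (300 simulated trials, 400 resamples each), a nominal 95% interval for the change in ω excluded zero in 9% of trials at 22% v 13% and b = 1, nearly all in the masking direction. For a commoner outcome, 50% v 25% (assumed), it did so in 25% (b = 1) and 48% (b = 1.5). An interval for the product of paths did so in about 5–7%.

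**Identity link.** For least squares on the same women and covariates, ω_tot - ω = a*b exactly, where a and b are here the treatment-to-stress and stress-to-outcome paths (the plan's α and β). The proportion sentence is correct. For the decision clause, simulations with N = 162, a standardised direct effect of 0.39 and no mediation gave:

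| Rule | Met with no mediation |
|---|---|
| ω still significant and reduced, read alone | about 50% |
| Also requiring significant total effect, α path and β path | 0.1–2.7% |

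The 50% arises because, with no mediation, the sign of the change in ω is a coin toss.

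**The case against.** A reader might infer that the plan has no test of mediation and so will declare it falsely half the time. The documents do not support that. Baron and Kenny is named as the method, power is calculated on the α and β paths with a program for that method, and bootstrap intervals are planned. Within that framework the clause separates partial from complete mediation. The power section fits this: under the assumed scenario 1 paths the clause alone is met in only about 37–38% of trials, so the stated power of more than 80% cannot refer to it. The 50% figure describes a reading that the named method does not invite. What remains is that the text never links the conclusion to the path tests or to an interval.

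A reader might also infer that non-collapsibility will manufacture mediation for binary outcomes. It will not: the shift is away from zero, so by itself it cannot produce a reduced ω.

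Three further points count against the size of the problem:
- The distortion is small if stress is a weak predictor. At 0.5 log-odds per SD, the plan's proportion is within about a point of the risk-scale share. The largest errors need 1.5 per SD, an odds ratio of about 4.5, which nothing in the documents supports.
- At 22% v 13% with 54 and 108 women, the standard error of the log OR is √(1/11.88 + 1/42.12 + 1/14.04 + 1/93.96) = 0.44 and power for the total effect is about 31%. The first Baron-Kenny step would usually fail for pre-term birth. With marginal rates fixed, the shift at b = 0.5 to 1.0 is 0.02 to 0.09, or 5–21% of that standard error.
- Birth weight, gestation, NBAS, Bayley, temperament and cortisol are continuous, so the logistic error does not reach them.

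These points limit the consequence. They do not make the logistic estimator valid.

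**Conclusion.** The concern holds for the logistic link. As written, the proportion mediated for pre-term birth and low Apgar scores is not a proportion mediated. With no mediation it is about -3% to -4%, -12% to -14% or -27% to -31% at 0.5, 1.0 or 1.5 log-odds per SD of stress, with a placebo risk of 16–22%. With real mediation it falls below the indirect share on its own log-odds scale. These sizes rest on an assumed strength of the stress effect and a normally distributed stress measure; the direction does not depend on the values chosen.

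For the identity link the estimator is sound and only the wording of the decision clause needs attention: about 50% false positives if read alone, under 3% with all steps enforced.

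It would go too far to say that Hypothesis 3 as a whole is invalid or that its power statement is wrong. The group comparisons under Hypotheses 1 and 2 are unaffected. The change should be made because the stated estimator is incorrect for a planned class of outcomes and the correction is cheap.

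**What to change.** Amend the Hypothesis 3 analysis text before unblinding, in three places:

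1. Restrict the change-in-ω proportion to the identity link, with both models fitted to the same women and covariates.
2. For binary outcomes, define the indirect effect on a collapsible or counterfactual measure. One option is natural direct and indirect effects on the risk scale, obtained by standardising over the fitted outcome and mediator models. Other valid measures would serve, provided that one is named in advance.
3. State that mediation is concluded only if the bootstrap interval for the named indirect effect (a*b for continuous outcomes) excludes zero. Keep the still-significant clause only to describe mediation, once shown, as partial.

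The cost is a few sentences and modest programming. No new data or participants are needed, and bootstrapping is already planned. With about 26 pre-term births expected at the pilot rates (0.22 × 54 + 0.13 × 108 = 11.9 + 14.0), the binary-outcome intervals will be wide, and the plan should say so.

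### The >80% power stated for Hypothesis 3 fits the mediated effect, not the small direct effect of scenario 1, where power is about 21–38%

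*Combined protocol and SAP*

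**What the plan says.** Hypothesis 3 is that the link between supplementation and infant outcomes is partially mediated by maternal stress. On method: "Mediation will be tested using the Baron and Kenny approach". The model regresses the infant outcome on maternal stress M and treatment T, with ω the coefficient of T. The change in ω when M is added estimates the share of the effect explained. If ω "is still significant but the magnitude is reduced, this would provide evidence for partial mediation". Bootstrap confidence intervals will also be examined to gain power, but the quantity they apply to is not named.

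The power section states that "162 subjects will provide sufficient power (>80%) to detect the following effects based on Cohen's criteria". It cites a published simulation study and a Baron-Kenny program, and then refers to Figure 6 and Table 2. The sample is said to be large enough "to detect medium effects for the α and β paths" together with "small effects for the direct effect (scenario 1"), or alternatively "small-medium effects for the α and β paths and medium effects for the direct effect (scenario 2").

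The Hypothesis 2 power section fixes the setting: "With 108 participants in the supplement group and 54 in the placebo group", and "using a two-sided test at the 0.05 significance level". Neither allocation nor significance level is restated for Hypothesis 3.

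**The concern.** In the power sentence the small direct effect is one of the things to be detected, alongside the α and β paths. It is not presented merely as a background condition of the scenario. A reader will take it that the trial has more than 80% power to find that effect significant.

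This matters because the one criterion the plan describes for partial mediation depends on the same coefficient remaining significant after adjustment for M. If its power is low, a trial in which partial mediation is real would usually fail that criterion. A non-significant ω could then be misread as full mediation or as no evidence.

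**Working it through.** **Inputs.** From the plan: N = 162 (108 and 54). Assumed: two-sided 0.05 for Hypothesis 3, a continuous outcome with a linear model, no dropout, and numerical values for small and medium. Three scales were tried, since the readable text gives none:

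- Standardised coefficients 0.14 (small), 0.26 (small-medium), 0.39 (medium). The outer two are √0.02 and √0.15, taking Cohen's f² as 0.02 and 0.15.
- Correlation-type coefficients 0.10, 0.20, 0.30.
- Cohen's d of 0.20, 0.35, 0.50 for the two paths starting from the randomised group, with β = 0.39 (medium) or 0.26 (small-medium).

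**Step 1: the plan's other figures reproduce.** For two groups the noncentrality is d × √(108 × 54 / 162) = 6d.

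- Infant temperament (ICQ): d = 3.7 / 7.8 = 0.474; 6d = 2.85; power 81%, against 80% stated.
- Infant cortisol: d = 0.19 / 0.4 = 0.475; power 81%, against 80% stated.
- Correlation (Hypothesis 1): atanh(0.22) × √159 = 2.82; power 81%, against 80% stated.

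Inverting, 80% power needs d = (1.96 + 0.84) / 6 = 0.47, or a coefficient of 2.80 / √162 = 0.22. These are before any allowance for correlation between T and M, which raises them. This alone shows the difficulty: anything labelled small would have to be as large as the differences on which the plan powers Hypotheses 1 and 2.

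**Step 2: power for the small direct effect.** Adjusting for M inflates the variance of ω by 1 + α²·Var(T), where Var(T) is 1 for standardised T and 2/9 for a 2:1 binary group.

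- d = 0.20: 6 × 0.20 = 1.20, power 22%. With α at d = 0.5, inflation is 1 + 0.25 × 2/9 = 1.056; 1.20 / √1.056 = 1.17; power 21%.
- r = 0.10: power 24–25% unadjusted. With α = 0.30, 0.10 × √(162 / 1.09) = 1.22; power 23%.
- Coefficient 0.14: 0.14 × √162 = 1.78, power 43%. With α = 0.39, 1.78 / √1.152 = 1.66; power about 38%.

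**Step 3: the mediation tests, by simulation** (20,000 runs, N = 162). The steps column requires α, β and the total effect all to be significant. The last column also requires ω to be significant and reduced. Ranges cover continuous T and standardised 2:1 binary T.

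| Scenario; α, β, direct | Direct effect alone | α and β jointly | Baron-Kenny steps | Steps plus ω significant and reduced |
|---|---|---|---|---|
| 1; 0.39, 0.39, 0.14 | 37–38% | 99.6% | 92–93% | 37–38% |
| 1; 0.30, 0.30, 0.10 | 23% | 93% | 59% | 20% |
| 1; d 0.5, 0.39, d 0.2 | 21% | 84% | 53% | 17% |
| 2; 0.26, 0.26, 0.39 | 99.7% | 81–82% | 81–82% | 80–81% |
| 2; 0.20, 0.20, 0.30 | 96% | 50–51% | 49–51% | 47–49% |
| 2; d 0.35, 0.26, d 0.5 | 84% | 49% | 47% | 40% |

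On the first scale the steps reproduce the stated level in both scenarios; a repeat simulation gave 93% and 80%. In scenario 1 the last column is held down by the direct effect alone.

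**Step 4: size needed for 80% on the small direct effect.** Coefficient 0.14: 2.80² × 1.152 / 0.14² ≈ 460. d = 0.20 at 2:1: 2.80² × 4.5 × 1.056 / 0.20² ≈ 930.

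The planned recruitment of 168 (112 and 56) changes little: √(112 × 56 / 168) = 6.11 in place of 6, so the unadjusted power for d = 0.20 becomes 23%.

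**The case against.** The strongest defence is that the figure was never meant as power for ω. The plan names the Baron and Kenny approach and cites a program for it. With the direct effect treated as a condition of the scenario, the stated level reproduces in both scenarios on a Cohen-based scale, and scenario 2 lands almost exactly on 80% at N = 162. That stands, and it rules out several stronger conclusions that a reader might draw.

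- *That the power was miscalculated.* The documents do not show this. The likelier fault is a sentence that does not say which test the figure covers.
- *That scenario 2 is also wrong.* It falls short only on scales chosen for this check. On the scale that reproduces the claim, even the criterion that includes ω has about 80%.
- *That no effect sizes are given.* Figure 6 is missing from the text as extracted and may carry them.
- *That significance of ω is the only route to a mediation claim, or that the plan promises 80% for that criterion.* The plan says such a result would provide evidence. It also uses the change in ω as an estimate and foresees bootstrap intervals. The power figure and the criterion stand in separate sentences.

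What the defence does not remove is the wording itself, which puts the small direct effect under the >80%. Bootstrap intervals for the indirect effect would not raise the power of the test on ω either.

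**Conclusion.** The point holds as a mismatch between the stated power and the stated target. In scenario 1, power for the small direct effect is about 21–38%, not more than 80%, and the described evidence for partial mediation would be met in about 17–38% of trials. True partial mediation of that size would miss the criterion in more than 60% of them.

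The exact figures rest on the assumed meaning of small and medium, on a two-sided 0.05 level carried over from Hypotheses 1 and 2, and on linear models without dropout. The direction does not depend on the choice of scale, because the plan's own calculations put the 80% threshold at d of about 0.47 or r of 0.22. The consequence is limited to a mechanistic hypothesis; sample size and randomisation are unaffected.

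**What to change.** In Power Calculations for Hypothesis 3, state that >80% refers to the mediated (indirect) effect, name the test and the effect-size scale it was computed on (by reference to Figure 6 if they stand there), and add that power for a small direct effect in scenario 1 is about 21–38%.

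In the Hypothesis 3 analysis, specify that the planned bootstrap confidence interval is for the indirect effect, and base the mediation conclusion on it. Report the direct effect as an estimate with its interval, without requiring it to be significant.

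The cost is a change of wording in two places and one less favourable stated figure. No extra participants or data are needed.

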In addition to associations between DHA supplementation and prenatal stress, we observed significantly higher birth weights among neonates born to women receiving DHA compared to placebo controlling for gestational age (3,174 grams versus 2,889 grams, p = .018) and greater likelihood of having a 1-minute Apgar score of 9 (odds ratio = 5.99 [95% Cl = 1.25 - 28.75], p = .025, controlling for birth weight and gestational age). Finally, 13% of neonates of mother receiving DHA supplementation were born prior to 37 weeks, compared to 22% of mothers received placebo; a difference that did not reach the level of statistical significance in the pilot study, but is clinically meaningful.

In summary, the data from our preliminary study are compelling in terms of the potential impact on health disparities in maternal and infant health, a significant public health problem that is poorly understood. We now seek to expand on these preliminary findings by conducting a more rigorous assessment of prenatal DHA supplementation on maternal and infant health by increasing the number of participants to 162, beginning supplementation earlier in pregnancy, adding additional measures of maternal health and stress response during pregnancy, increasing the frequency of assessment, assessing DHA levels in red blood cells at each visit, and including multiple postnatal assessments of infant neurodevelopment. The proposed study offers an opportunity for replication and to test the impact of supplementation on infant functioning and, if effects are observed, whether they are mediated by changes in prenatal stress.

APPROACH

Participants

One hundred-sixty-eight pregnant, African American, women will be recruited from the University of Chicago obstetric clinic. Inclusion criteria will include: age between 18 and 34 years, household receipt of public assistance (e.g., Medicaid insurance) due to low-income, and low levels of DHA consumption as defined as less than two fish servings per week. Exclusion criteria are reports of known medical complications, regular use of steroid medications, alcohol, cigarettes, or illegal substances (by maternal report), use of blood thinners or anti-coagulants, use of psychotropic medications, BMI >40, and allergy to iodine and/or soy. Participants may be excluded if medical complications arise after enrollment. Neonates with significant medical complications will be maintained in the study.

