There are two reasons for our focus on African American women. First, as described above, African American women are disproportionately represented among families living in inner-city poverty and have the highest rates of suboptimal birth outcomes in the U.S. (Giscombé & Lobel, 2005). Second, there are racial differences in cortisol reactivity to

stress and pregnancy (De Santis et al., 2007; Glynn et al., 2007; Wilcox et al., 2005) and in the genes regulating cortisol (Baerwald et al., 1999). Given the scope of the proposed study and the potential to generate data that can be translated into reductions in health disparities, we chose to study African Americans only, but acknowledge that it will be important to test racial and ethnic differences in maternal and infant response to DHA supplementation during pregnancy.

Women will be randomly assigned to receive the omega-3 nutritional supplement (n = 112) or a corn and soybean oil placebo (n = 56) beginning at enrollment and up through the end of pregnancy. In the proposed design we allocate the number of participants to groups to optimize power to test the hypotheses. We expect greater variability in the independent measure (i.e. DHA level) and dependent measures (e.g., stress reactivity) in participants in the experimental group than those in the control group given anticipated differences in uptake and metabolism. Thus, we plan to enroll a higher number of participants in the experimental group than in the control group to adequately capture that variability (Cox, 1958). Participants and investigators will be blinded to the group to which they have been assigned. Treating clinicians will identify demographically eligible participants who will be contacted by research staff for further screening. Participants who meet the inclusion and exclusion criteria will then be scheduled for the baseline visit.

Participants will be reimbursed on an accelerated schedule with \$100 for their first visit and an increase in payments by \$25 for each subsequent visit, ending with a \$250 payment for the last post-partum visit. Participants will receive incentives in between visits including water bottles, tote bags, newborn t-shirts, etc. They also will be reimbursed with \$10 to cover travel costs for each visit.

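### LOCF is the main missing-data method although the pilot effect appeared only late in pregnancy, and the intent-to-treat sentence does not cover women excluded for complications after enrolment

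*Combined protocol and SAP*

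**What the plan says.** The Missing data section opens: "Missing data is not expected to be a major issue based on retention rates from the preliminary study". It then sets the method: "The last observation carried forward (LOCF) approach for missing data will be employed". The only check is this: "Sensitivity analyses using complete-cases only will also be performed and the results using the two approaches compared". On the analysis set it says that "treatment non-compliers will be included in the primary analysis based on the intent-to-treat (ITT) principle".

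Under Approach, Participants, the plan states: "Participants may be excluded if medical complications arise after enrollment". The next sentence treats infants differently: "Neonates with significant medical complications will be maintained in the study". The assigned product is taken "beginning at enrollment and up through the end of pregnancy", so an exclusion after enrolment can follow randomisation. No section says whether an excluded woman leaves supplement, follow-up or the analysis.

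Hypothesis 1 tests perceived stress and inflammatory markers by repeated measures ANOVA, with the group-by-time interaction singled out. A mixed-effects model appears only for stress reactivity, as a comparison with an ANOVA run separately at each visit. Hypothesis 3 takes its mediator from the final prenatal visit.

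**The concern.** LOCF sets a woman's change after her last observed visit to zero. The sponsor's own pilot (Preliminary support for hypotheses) found no difference between arms in perceived stress or cortisol response at 24 weeks and a difference in both at 30 weeks. The Maternal Stress Response section adds that stage of pregnancy itself affects cortisol. Carrying an earlier value into the last visit can therefore shrink a real late effect.

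If the share carried forward differs by arm, LOCF can also create a difference or hide one. One route is delivery before the 34-36 week visit. Pilot preterm birth was 13% on supplement and 22% on placebo; that difference was not significant, and only some of those births would precede the visit.

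The complete-case check is in general unbiased only if data are missing completely at random. If it disagrees with LOCF, the comparison does not show which is right.

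The exclusion sentence raises a separate issue. Complications in pregnancy may lie on the path to gestational age and birth weight, which are Hypothesis 2 outcomes. If the sentence is applied to follow-up or analysis, those comparisons are no longer between the groups as randomised.

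**Working it through.** **1. The plan's own figure.** Inputs from Power Calculations for Hypothesis 1: 108 and 54 women, means 27.5 and 29.3 (difference 1.8), SDs 3.4 and 3.1, two-sided 0.05.

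- Pooled SD = √[(107 × 3.4² + 53 × 3.1²)/160] = 3.30
- Standard error = 3.30 × √(1/108 + 1/54) = 0.551
- Noncentrality = 1.8/0.551 = 3.27
- Power of the pooled t-test = 90.1%

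The stated figure (above 90%) reproduces. It assumes that all 162 women have an observed value at that visit.

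**2. How much may be missing.** All inputs are from the pilot results.

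- Withdrawn: 4/64 = 6.3%.
- Attended all three sessions: 47/64 = 73.4%, so 26.6% missed at least one.
- The 30-week perceived-stress test has 47 error degrees of freedom. With an intercept, group and two covariates, n = 47 + 4 = 51. Then 13/64 = 20.3% are absent from that analysis.

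Power is computed on 162, while the plan says "One hundred-sixty-eight pregnant, African American, women will be recruited". If the 6 extra women are the loss allowance (an assumption, as the documents do not say), it is 6/168 = 3.6%.

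**3. Effect on the last-visit comparison.** Let m be the share of final values carried forward, equal in both arms, and f the fraction of the final effect already present at the carried visit. With the SD unchanged, the expected LOCF difference is 1.8 × [1 − m(1 − f)] on 108/54. Complete cases keep 1.8 on (1 − m) of the women. With m = 0.20:

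| Analysis | Expected difference | Power |
|---|---|---|
| LOCF, f = 0 | 1.44 | 74% |
| LOCF, f = 0.5 | 1.62 | 83% |
| LOCF, f = 1 | 1.80 | 90% |
| Complete cases (86.4/43.2) | 1.80 | 83% |

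The two methods have equal power at f = 0.465; below that, LOCF is worse. With m = 0.10, LOCF gives 83%, 87% and 90%, and complete cases give 87%. With 112/56 and m = 0.20, LOCF gives 75%, 85% and 91%, and complete cases give 84%.

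**4. A likelihood-based alternative.** Simulation with 4,000 runs, two visits, common SD 3.3, 20% of final values missing completely at random, and assumed visit correlation 0.5 to 0.7. The likelihood estimate was 1.79 to 1.81 for f = 0, 0.5 and 1, with power 83% to 86%. LOCF estimated 1.43, about 1.62 and about 1.80.

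**5. Unequal missingness.** Suppose there is no treatment effect, both arms drift by 2 points between visits, and 6.3% and 26.6% are carried forward (all assumed, and the gap between arms is wide). The LOCF bias is 2 × (0.0625 − 0.266) = −0.41. With SD 3.4 in both arms the rejection rate is about 11% instead of 5%. Drifts of 1 and 3 points give 6.5% and 19%.

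In a further simulation, missingness depended on arm and on outcome values, and the true difference was 1.8. LOCF averaged 1.65 to 2.03 and complete cases 1.40 to 1.53, while the likelihood estimate stayed near 1.8. These sizes depend on the assumed mechanism and are illustrative.

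**6. Exclusions.** No arithmetic applies. Women with complications may be excluded and infants with complications are kept. The intent-to-treat sentence names non-compliers, and a woman excluded for a complication is not necessarily one.

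**The case against.** The pilot pattern may not carry over. This trial starts supplement earlier, and the visit before the last, at 24-30 weeks, could follow roughly as much supplementation as the pilot women had at 30 weeks. If duration drives the effect, that visit may hold most of it, and LOCF then matches or beats complete cases over more than half of the range of f. This stands: the direction and size of the LOCF error are unknown. But that is a reason not to let the main estimate depend on it.

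Under data missing completely at random, complete cases are unbiased too, and the mixed model gains only about 0 to 3 points of power over them. This also stands. The stronger argument is missingness that depends on arm or earlier values, where complete cases can fail as well.

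The power figures are for a two-sample comparison at one visit, not the planned repeated measures ANOVA. That is true, but the plan's own power statement is framed the same way.

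The 20% is inferred and could include women who attended but lacked a questionnaire. Visit payments are also larger here than in the pilot, which may help retention. At 10% missing the worst LOCF case is 83% against 87% for complete cases, so the loss is smaller but not absent.

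The mixed model already in the plan does not fill the gap: it is secondary and works within each visit, and it does not cover perceived stress.

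Finally, exclusion may mean only stopping supplement or testing, and the intent-to-treat principle could be read broadly. That is possible, so this part is an ambiguity to close, not a shown bias.

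**Conclusion.** The concern holds and should be fixed. With 20% of final values carried forward equally in both arms, the LOCF estimate of a true 1.8-point difference lies between 1.44 and 1.80, and power between 74% and 90%, according to an unknown that the plan cannot resolve. Unequal missingness can bias the result in either direction. The pilot does not support treating missing data as minor.

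The reading of the text is firm. The size rests on the inferred 20%, an unchanged SD and a single-visit test. LOCF does not affect single-time outcomes such as birth weight. It does affect the repeated prenatal measures and the final-visit mediator of Hypothesis 3. The exclusion point is secondary: the text permits removal of women after randomisation without saying that it will happen.

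**What to change.** - For outcomes repeated across visits, make the main analysis a likelihood-based mixed model for repeated measures on all observed visits, with arm-by-visit terms and the baseline value as covariate where one exists.
- Drop LOCF or demote it to a sensitivity analysis. Report missing visits by arm.
- State that every randomised woman is followed and analysed as randomised whatever complications arise, with birth outcomes still taken from the medical record. Report any exclusions by arm. Whether supplement or stress testing continues is a separate clinical decision.

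The cost is protocol and SAP wording and slightly more modelling; the plan already takes birth outcomes from the medical record. There are two drawbacks. The mixed model assumes data are missing at random. If the carried visit already held the full effect, the model would have less power than LOCF (83% to 86% against 90%).
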